#### 10.2 Confidentiality

Patient information will be kept confidential and managed according to the 1996 HIPAA guidelines. All patient information will be de-identified and stored in a secure, locked environment. Each patient will be given a unique subject number and will be identified by this number and their initials. All data used in the analysis and reporting of this evaluation will be without identifiable reference to the patient. Data relating to the study might be made available to third parties (for example in case of an audit performed by regulatory authorities) provided the data are treated confidential and that the patient's privacy is protected.

#### **10.3** Deviations from Protocol

The investigator will not deviate from the protocol except in medical emergencies or in unforeseen, isolated instances where minor changes are made that will not increase the patient's risk or affect the validity of the trial. In medical emergencies, prior approval for protocol deviations will not be required, but the IRB/EC must be notified within five days of the incident.

#### **10.4 Withdrawal of Subjects**

A subject may withdraw from the study at any time should they choose to do so. Additionally, subjects may be withdrawn by the investigator if deemed appropriate due to safety or compliance issues.

#### **10.5 Economic Impact on Subjects**

The catheter-based renal sympathetic denervation procedure is part of a research study and is investigational. The cost of the renal sympathetic denervation procedure and follow-up will be the responsibility of the subject or the subject's insurance carrier. No payment will be made to the subject for taking part in this study.

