# **PROTOCOL SUMMARY**

Title:	RESET-VT			
Objective:	The goal of this trial is to test the impact of catheter-based renal sympathetic denervation (RSDN) as an adjunctive treatment for patients with either ischemic or non-ischemic cardiomyopathy undergoing catheter ablation of ventricular tachycardia (VT). The proposed study is a prospective, multicenter, randomized control trial. Patients undergoing VT ablation will be randomized to either VT ablation alone or VT ablation + RSDN.			
Design:	This study is a prospective, multicenter, single-blinded, randomized (1:1) control trial evaluating the effectiveness of RSDN in the prevention of recurrent VT in patients with ischemic or non-ischemic ventricular dysfunction who are undergoing catheter ablation for VT. These patients will be randomized to ablation alone or ablation + RSDN. Subjects will only be eligible for this study if they are $\geq$ 18 years of age and have a history of structural heart disease (post-MI, dilated cardiomyopathy, sarcoid myopathy, hypertrophic cardiomyopathy, etc.), have an existing ICD and are planned for catheter-based VT ablation. In addition, eligible patients will have accessible renal vasculature (as determined by renal angiography). The patient will be blinded to the results of randomization. Once randomized, study group subjects will undergo a strategy of catheter-based renal sympathetic denervation + VT ablation. Follow-up will be conducted in regular intervals over a 24- month period.			
Enrollment:	Total: 202 subjects			
	Pilot Phase: 20 subjects (~10 control group, ~10 study group)			
Clinical Sites:	
 
Mount Sinai School of Medicine (PILOT)
 
Homolka Hospital, Prague, Czech Republic (PILOT)
 
Other Sites TBD (total up to 25 sites)
 
			
Time Course:	Initial enrollment: December 2012			
Renal VT Version 1.3 November 2012				

	Last enrollment: July 2013 (Pilot) Last 24-month follow-up: July 2015 (Pilot) Eligible subjects include those ≥ 18 years of age with a history of structural heart disease (post-MI, dilated cardiomyopathy, sarcoid myopathy, hypertrophic cardiomyopathy, etc.), have an existing ICD and are planned for catheter-based VT ablation. In addition, eligible patients will have accessible renal vasculature (as determined by renal angiography).				
Subject Description:					
Study Group:	In addition to VT ablation, the subjects in this group will undergo catheter-based renal sympathetic denervation.				

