Control Group:	Subjects in the control group will undergo a standard procedure for catheter-based VT ablation.				
Primary Endpoint:	
 
Time to first event requiring appropriate ICD therapy for ventricular arrhythmia or Incessant VT (VT occurring below the ICD rate cut-off)
 
				
Secondary Endpoints:	
 
Appropriate ICD therapy for ventricular arrhythmia
 
Appropriate ICD Shocks ventricular arrhythmia
 
Inappropriate ICD therapy
 
All ICD therapy (Appropriate + Inappropriate)
 
A composite of Mortality, ICD storm, and Incessant VT (VT occurring below the ICD rate cut-off)
 
Number of Hospitalizations for Cardiovascular Causes.
 
Total VT burden (Number of episodes).
 
All-Cause Mortality.
 
The occurrence of ICD storm, defined as ≥3 appropriate shock therapies within 24 hours.
 
Differences in blood hormone measurements (including norepinephrine, aldosterone, renin, and BNP).
 
Differences in Cardiac parameters, including LV size (septal and free wall thickness) and mitral inflow (E&A velocity), as measured by trans-thoracic echocardiography.
 
Procedure related adverse events including, but not limited to hematomas, pseudoanuerysms, renal artery stenosis, renal impairment, thromboembolic events, stroke, pericardial bleeding including tamponade and myocardial infarction
 
Change in blood pressure
 
				

	
 
15. Development of orthostatic hypotension
 
16. Other individual complication rates including, but not limited to MI and death.
 
17. 30-day Major Complication Rate defined as death, stroke, MI or any other serious adverse events related to the treatment or procedure within the first 30 days or through hospital discharge (whichever is longer);
 
18. Procedure time
 

Primary Analytical Analysis:	Intent to treat analysis
Secondary Analytical Analysis:	Per protocol analysis
Principal Investigator:	[name]. Mount Sinai School of Medicine [name]
Site, Monitoring, and Data Management Center	Electrophysiology Clinical Research Group Mount Sinai School of Medicine [name]
Data Safety and Monitoring Board:	TBD

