### 9. Pre-Procedure and Ablation Study Design Flow-Chart

#### **PRE- AND ABLATION PROCEDURE**

### 9.1.1 **PRE-PROCEDURE**

The following tests and procedures will occur before the ablation:

- Recording of patient medical history (including details of VT both clinical/ICD)
- Recording medication history (including all AAD ever used, duration of use)
- Obtain β-HCG in females of child bearing age the morning of the procedure as per usual clinical practice
- Baseline assessment of arrhythmia burden and type: Office/inpatient records, ICD interrogation report
- Baseline NIH stroke scale
- If performed for any reason, collect any pre-procedural imaging: MRI/CT and Renal Ultrasounds within 6 months of procedure
- Baseline laboratory, including complete blood count, standard electrolyte panel, renal function, and brain natriuretic peptide levels.
- Baseline Transthoracic Echocardiogram
- Baseline blood pressure. Proper blood pressure measurement technique is essential: i) patient should sit quietly in a chair with his/her back supported for 5 minutes before taking the measurement; ii) use of the correct cuff size with the air bladder encircling at least 80% of the arm (the adult large cuff for the majority of patients); iii) support the arm at heart level during the cuff measurement; iv) a minimum of 2 readings should be taken at intervals of at least 1 minute and the average of those readings should be taken to represent the patient's blood pressure; v) the blood pressure should be measured
- Consent must be obtained before the VT ablation procedure.
- Randomization into one of two groups will be performed by opening the Randomization envelope after Renal Angiography.

Study/Experimental Group: These subjects will undergo catheter-based sympathetic renal denervation.

Placebo Control Group: These subjects will receive no further intervention..

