#### 9.1.3 VT ABLATION PROCEDURAL DETAILS

- Patients will be brought to the electrophysiology laboratory in a fasting state
- General anesthesia/conscious sedation will be used according to operator preference
- Patients will undergo electrophysiology study and VT ablation as per standard practice
- Therapeutic anticoagulation will be administered with intravenous heparing with a target ACT of 300 seconds or greater.

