#### 9.1.4 RENAL SYMPATHETIC ABLATION PROCEDURAL DETAILS

• In patients randomized to receive RSDN, the procedure will be performed after the VT ablation on therapeutic anticoagulation with intravenous heparin.

- Abdominal aortography will be performed to assess the renal arteries for the suitability of catheter-based renal denervation in all patients. For those patients in whom the angiogram demonstrates that the renal anatomy is inappropriate for the RSDN procedure (small renal arteries, extensive atherosclerosis, renal stenosis, etc), the patient will be excluded from the study as a screen failure. The patient's baseline information will be collected but no further follow-up required (beyond assessing for any adverse events related to the procedure). If the renal arteries are deemed suitable for RSDN, the patient will then undergo randomization.
- Randomization will be done by permuted-block randomization centrally and will be stratified by site. Allocation concealment shall be maintained at all sites by the use of a web-based central randomization scheme. The operating physician controlling the delivery of ablative energy will be aware of the outcome. This approach has been selected to minimize (1) study bias and (2) placebo effect. The randomization schema will be blocked by size for each site.
- After confirmation of eligibility, an irrigated radiofrequency ablation catheter will be introduced sequentially into each renal artery.
- The ablation catheter is placed within a long vascular sheath and advanced into the renal artery. The sheath is advanced over the catheter to engage the renal artery ostium and allow for contrast injection and visualization of the vessel during catheter manipulation.
- After completion of the measurement, no more than six radiofrequency ablation lesions separated both longitudinally and rotationally (a —spid pattern", see figure) will be placed per renal artery. The power will be started at 10 W and titrated to a maximum 20 W, as deemed appropriate by the impedance drop (goal 10% drop). Each lesion should be between 30-120 seconds in duration (no more than 120 seconds per lesion).

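### The patient blind is not protected: section 10.5 charges RSDN, given in one arm only, to the subject or insurer, and no masking of the bill or the procedure is described

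*Combined protocol and SAP*

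**What the plan says.** The Design entry of the Protocol Summary states: "The patient will be blinded to the results of randomization". Section 2 also calls the trial single-blind. The operator is not masked; section 9.1.4 says: "The operating physician controlling the delivery of ablative energy will be aware of the outcome".

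Four other provisions bear on whether the patient's mask survives:

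- Section 10.5, on payment: "The cost of the renal sympathetic denervation procedure and follow-up will be the responsibility of the subject or the subject's insurance carrier".
- Section 9.1.3, on the VT ablation: "General anesthesia/conscious sedation will be used according to operator preference".
- Section 9.1.4, on sequence: "In patients randomized to receive RSDN, the procedure will be performed after the VT ablation".
- Section 9.1.1, on the arm it labels a placebo control: "These subjects will receive no further intervention".

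Controls are not untreated. The Protocol Summary says: "Subjects in the control group will undergo a standard procedure for catheter-based VT ablation". Section 9.1.4 adds, for both arms and before randomization: "Abdominal aortography will be performed to assess the renal arteries for the suitability of catheter-based renal denervation in all patients".

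**The concern.** The patient is the only party whom the protocol declares blinded, and following its own rules can undo that blind by two routes. A bill or insurer's statement that names renal denervation tells the patient which arm they are in. A patient under conscious sedation may also notice a further stage of catheter work and energy delivery for which the control arm has no counterpart.

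Patients who know their arm may differ in drug adherence, in what they report, in when they seek hospital care and in whether they stay in the study. They may also tell follow-up staff, whom the protocol does not describe as blinded, and section 9.2.2 leaves much of the cardiovascular medication to the investigator's discretion. If the blind fails unobserved, the trial would report a patient blind that it did not have.

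**Working it through.** The claim rests mainly on setting provisions side by side. The little arithmetic available bounds its size.

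**1. Is the charge specific to one arm?** Both arms have VT ablation and renal angiography. After randomization the planned difference is RSDN alone, so a charge for RSDN can arise only in the study group. The clause in 10.5 also mentions follow-up, but Table 1 does not split follow-up by arm, so I rely on the procedure charge only.

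**2. Does anything keep that charge from the patient?** Neither section 10.5 nor the procedure, follow-up and data-handling sections delay it, mask it or route it elsewhere. Nor do they say whether a bill is itemised, who sees it or when it is issued.

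**3. Can the procedure itself disclose the arm?** Conscious sedation is allowed, RSDN follows the VT ablation, and no sham step is described for controls. The sedation line stands in the VT ablation section and 9.1.4 gives no separate rule, so applying it to RSDN is an inference. Section 9.1.4 allows up to 6 lesions per artery, each of 30 to 120 seconds:

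- lesions at the maximum count: 6 × 2 arteries = 12
- at 30 s each: 12 × 30 = 360 s = 6 min
- at 120 s each: 12 × 120 = 1,440 s = 24 min

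Six lesions is a ceiling, so 6 minutes is not a lower bound; fewer lesions take less time. The 24 minutes is the most that energy delivery alone could take, without catheter placement. No provision links this time to what a patient would perceive.

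**4. How many patients could be unmasked?** Section 7 plans 202 patients, of whom about 18 screen out after angiography: 202 − 18 = 184, and 184 / 2 = 92 per arm, as stated there. The documents give neither the share billed directly nor the share under conscious sedation. With an assumed share *p* of RSDN patients unmasked by either route, the number is 92 × *p*:

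| Assumed *p* | RSDN patients unmasked |
|---|---|
| 0% | 0 |
| 25% | 23 |
| 50% | 46 |
| 100% | 92 |

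I put no figure on controls. A control would have to expect a charge, notice that none came and read its absence correctly.

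**5. Which endpoints are exposed?** ICD therapy is read from device interrogation, section 9.2.3 sets programming for both groups, and under 9.3.2 two independent electrophysiologists adjudicate all ICD events, although their own blinding is not stated. Patient knowledge has limited reach there. Incessant VT below the rate cut-off is less clearly covered, because the committee's stated remit is ICD events. More open to patient knowledge are cardiovascular hospitalisation, blood pressure, orthostatic hypotension and reported adverse events (section 5.2), together with co-medication, withdrawal (10.4) and the roughly 10% loss to follow-up expected in section 7. The sample size uses no input on blinding and is unaffected.

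**The case against.** The strongest reply is that nothing here shows that the blind fails. General anesthesia is also permitted, and the insurer may be the one billed, so some patients could stay masked throughout. Both arms undergo catheter work, contrast imaging and VT ablation, and a sedated patient who does not know what the other arm feels may not recognise an added final stage. The sample consent form is not in the text available and may contain wording on billing or blinding. The main endpoint is device-based and adjudicated.

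Most of this stands as a limit on the claim. A reader might infer that the blind cannot hold, that controls get nothing, or that bills reach everyone early in follow-up. The documents support none of these: masking is possible for some patients, controls receive VT ablation and aortography, and no billing date is given. A reader might also cite the remark in 9.1.4 about limiting bias and placebo effect as the rationale for the patient blind. It follows sentences on allocation concealment and operator awareness and may not refer to the patient, so I do not rely on it.

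What the reply does not remove is the conflict within the protocol body. It declares patients blinded, assigns to them or their insurers a charge that only one arm can incur, and describes no safeguard. Consent wording might soften that conflict but would leave the protocol sections unreconciled.

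**Conclusion.** The concern holds in this form: the patient blind is declared but not protected, and section 10.5 must be reconciled with the Protocol Summary and section 2. The billing conflict rests on the text directly. The sedation route is a reasonable inference from 9.1.3, 9.1.4 and 9.1.1. The size is unknown, from 0 to all of about 92 RSDN patients on the assumed range.

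A reader might infer that the primary comparison is compromised. The documents do not show that. The threat falls mainly on the patient-influenced secondary endpoints, on co-treatment and retention, and on the accuracy of calling the trial patient-blinded. This should be corrected, but it does not by itself undermine the ICD-therapy result.

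**What to change.** **(a) Procedure.** In 9.1.3 and 9.1.4, require for every subject under conscious sedation, in both arms, the same headphones, eye cover and neutral room script from renal angiography to the end of the procedure. No change to sedation is proposed. The cost is inexpensive equipment and a short instruction to staff.

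**(b) Billing.** Reconcile 10.5 with the Protocol Summary and section 2, so that no arm-identifying RSDN charge goes to the subject before the 24-month visit where billing rules allow. Controls must not be charged for RSDN, which rules out an identical RSDN charge line for both arms. The downside is that recovery of the charge is delayed, or the charge is absorbed, which may not be cheap. Where this cannot be done, stop describing the patients as blinded and interpret the patient-influenced endpoints accordingly.

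**(c) Check.** Ask each subject to guess the arm, with a don't-know option, at discharge and at 12 months, and report the answers by arm. The discharge answer is the cleaner test, since by 12 months a guess may reflect whether VT has recurred. This adds one question at two existing contacts.

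The package needs a protocol amendment and revised billing instructions, with no additional patients or visits.

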#### **11.0 ETHICAL AND REGULATORY CONSIDERATIONS**

**11.1** Risk to subjects: Although it is unlikely, it is possible there may be loss of confidentially. This is a typical risk of any research study. Stenosis, dissection, and groin complications are possible clinical risks however they are not anticipated risks in this trial.

**11.2** Potential Benefits to Subjects: After undergoing RSDN, patients may experience less episodes of VT requiring ATP or shocks a result of the expected reduction in whole body norepinephrine spillover and sympathetic nerve activity.

#### 11.3 Role of the Coordinating Center

As principal investigator and study sponsor of this clinical study, [name] assumes the overall responsibility for the conduct of the study, including assurance that the study meets national and institutional guidelines for study conduct. In this study, [name] will have certain direct responsibilities and will delegate other responsibilities to his staff at the Coordinating Center, the Mount Sinai Hospital. Together, the coordinating center will: 1) ensure adherence to the national and institutional regulations; 2) develop and distribute protocols and case report forms; 3) coordinate data organization; 4) perform statistical analyses.

#### 11.4 Maintaining Records (21 CFR 812. 140 (B))

The Coordinating center will maintain copies of correspondence, data, shipment of devices, adverse device effects and other records related to the clinical trial.

#### **11.5 Site Record Retention Policy**

All clinical sites will maintain study records for two years after research termination.

#### 11.6 Institutional Review Board (IRB) / Ethics Committee (EC) Information

This protocol and the informed consent must be reviewed and approved by the appropriate IRB/EC where the trial is to be conducted before enrollment of patients. Changes to the protocol that may increase the risk or present new risks to the patient, or may adversely affect the validity of the trial, must be approved in writing by the IRB/EC before the change is made.

The study site Principal Investigator(s) is responsible for submitting and obtaining initial and continuing review (at intervals not greater than once a year) of the trial by their IRB/EC.

#### **12.0 DATA HANDLING**

Information about patients will be kept confidential and managed according to the requirements of the United States of American Health Insurance Portability and Accountability Act of 1996 (HIPAA). Those regulations require a signed patient authorization informing the patient of the following:

1. What protected health information (PHI) will be collected from patients.

- 2. Who will have access to that information and why.
- 3. Who will use or disclose that information.
- 4. The rights of a research patient to revoke their authorization for use of their PHI.

In the event that a patient revokes authorization to collect or use PHI, the investigator, by regulation, retains the ability to use all information collected prior to the revocation of patient authorization. For patients that have revoked authorization to collect or use PHI, attempts should be made to obtain permission to collect at least vital status (i.e. that the patient is alive) at the end of their scheduled registry period.

In order to ensure patient confidentiality, all case report forms and patient information (CT / MRI, if reviewed), fluoroscopic and endoscopic images, ECGs) will be de-identified and replaced with a unique patient identifier. Information will be stored in the office of the local study coordinator, which will be kept in a secure location. The research study coordinators, principal investigator and co-investigators will be the only people with access to this data. All data will be stored without any patient information apart from the unique three digit patient identifier. There will be a code sheet that will link the de-identified data back to the subjects. This will be encrypted and password-protected. One copy will be stored in the primary investigator's computer, and another in the research coordinator's computer.

